-	Study Week		Week 0	Week 1	Week 2	Week 3	Week 4	Week 5	Week 6 or ET at week 6	Week 7	Week 8	Week 9	Week 10	Week 11	Week 12	Any visit other than at week 6
Medical His	tory	X														
Physical Ex	am	Х														
MINI		Х														
Pregnancy Test (Females only)		X														
Post-Screer Pregnancy Checklist	ning		X			Х			X			Х				
ECG		Х							Х						Х	Х
Labs (CMP, Panel, CBC CRP, IL6, T	, Hs- NFα)	X							X						Х	X (only CMP, Lipid panel, and CBC)
Lab (HbA10	C) ⁴	Х														
Vital Signs		X	Х	Х	Х	Х	Х	Х	Х	Х	Х	Х	Х	Х	Х	Х
Height		X	Х													
Weight		X	Х	Х	Х	Х	Х	Х	Х	Х	Х	Х	Х	Х	Х	Х
Waist Circumferer	nce		Х						Х						Х	
TLFB ¹		Х	Х	Х	Х	Х	Х	Х	Х	Х	Х	Х	Х	Х	Х	Х

VAS	Х	Х	Х	Х	Х	Х	Х	Х	Х	Х	Х	Х	Х	Х	Х
Urine Drug Screen	Х	Х	Х	Х	Х	Х	Х	Х	Х	Х	Х	Х	Х	Х	Х
Fagerstrom Test	Х							Х						Х	
Adverse Events		Х	Х	Х	Х	Х	Х	Х	Х	Х	Х	Х	Х	Х	Х
PANSS		Х						Х						Х	
SANS		Х						Х						Х	
CDRS		Х						Х						Х	
CGI-S and CGI-I ²		Х						Х						Х	
CSSRS	Х	Х						Х						Х	Х
QOL		Х						Х						Х	
EPS Scales (BAS, SAS, AIMS)		Х						Х						Х	
Drug dispensing		Х	Х	Х		Х		Х		Х		Х			
Supportive Counseling		Х	Х	Х	Х	Х	Х	Х	Х	Х	Х	Х	Х	Х	

1- TLFB at screening will be completed for the past 30 days. All other visits the TLFB will collect information for the past week.

2- CGI-I will not be administered at baseline. Only CGI-S is administered at baseline.

- 3- EOT end of treatment
- 4- Lab (HbA1C) will only be performed at the screening visit

5- If ET falls on week 6, the visit should follow regular week 6 protocol. If ET falls on any other visit, follow ET protocol

Informed Consent Process: All subjects will sign IRB approved informed consent form (ICF) prior to starting any study related screening procedures. The written informed consent will be obtained by authorized study personnel. The authorized study staff will explain the study objectives, risks and benefits and overview of the study procedures to all subjects as part of the consent process.

Eligibility Review: An eligibility review will be conducted by the investigator at each site as per the inclusion exclusion criteria listed in section D of the protocol. All subject eligibility criteria will be reviewed by UMass designee prior to subject randomization.

Demographics and Medical/Psychiatric History: Subject's demographics, medical and psychiatric history will be collected as part of the screening process. All patient medical and psychiatric history will be reviewed by the investigator.

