Pregnancy Tests: A urine dip stick pregnancy tests will be administered to all women at screening. The pregnancy test can be repeated at any time during the study as per PI discretion. All subjects must test negative for pregnancy tests to be eligible for the study.

Urine Drug Tests: All subjects must undergo urine drug tests for a panel of substances at every study visit. The urine drug test will be completed prior to administering the timeline follow-back (TLFB).

The urine drug screen will include opioids, cocaine, methamphetamines, cannabinoids, barbiturates, benzodiazepines, methamphetamine, and phencyclidine.

Supportive Counseling: Qualified staff will provide supportive counseling to study subjects at weekly visits. Brief supportive counseling sessions about substance use will be provided as part of study visits. The content and structure is adapted

from the Individual Resiliency Training (IRT) manual that was originally developed for the RAISE (Research to identify, optimize and personalize early treatment for people affected by schizophrenia) study (Mueser et al., Psychiatric Services 2015; 66:680-690). Counseling will be provided to all subjects. Counseling is not manualized and no fidelity check is planned. Counseling will focus on:

1) substance abuse counseling to encourage a reduction in or abstinence from alcohol consumption;

2) Medication management counseling to encourage compliance with the treatment.

Efficacy Assessments

Timeline Follow-back (TLFB): Substance use will be recorded using the timeline follow-back method at every study visit. At screening visit, TLFB will assess substance use and dollar amount spent on substances for the past 30 days. All other visits will collect substance use data and dollar amount spent in the past week or for the period between the last visit and the current visit. The subject's drug screen results will be conveyed to the subject prior to administration of the TLFB. If the subject's self-report is at odds with the drug screen results, then the subject's report will not be challenged. All reported data from the subject and drug test results will be collected and used in exploratory analyses

Visual Analog Scale (VAS): The VAS will be used to assess craving for substance use as per the schedule of events and administered as per the schedule of events. The VAS is a horizontal line with a unipolar scale, anchored on the right side with

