"No desire at all" (marked with a "0") and on the left side with "Worst imaginable desire" (marked with a "100" with a line connecting the two ends. Subjects will mark the appropriate point to indicate where their "desire for substance" falls on this line.

Fagerstrom Test: The Fagerstrom Test for Nicotine Dependence will be used to assess smoking status. Data on subjects will be collected using the Fagerstrom test as per the schedule of events.

Positive and Negative Syndrome Scale (PANSS): PANSS is a measure used to assess symptom severity in patients with schizophrenia. It consists of three sections: Positive scale has 7 items, Negative scale has 7 items and General

Psychopathology has 16 items. Each item (symptom) will be scored on a 7-point scale with higher scores representing increasing levels of psychopathology: 1) Absent, 2) Minimal, 3) Mild, 4) Moderate, 5) Moderate severe, 6) Severe, and 7) Extreme. The PANSS will be administered by a designated study staff at time points specified in the schedule of events.

Schedule of Assessment of Negative Symptoms (SANS): SANS is a 24-item scale used to assess negative symptoms based on observation and a structured interview in patients with schizophrenia. Designated study staff will administer the SANS at baseline, week 6 and week 12.

Calgary Depression Rating Scale (CDRS): The Calgary Depression Rating Scale is used to depression symptoms in subjects. The PI or a designated staff will administer the CDRS at baseline, week 6 and week 12.

Clinical Global Impression – Severity and Clinical Global Impressions – Improvement Scales (CGI-S and CGI-I): The CGI-S and CGI-I are observer rated scales. The CGI-S measures illness severity on a 7-point Likert scale 1) Normal, not at all ill, 2) Borderline mentally ill, 3) Mildly ill, 4) Moderately ill, 5) Markedly ill, 6) Severely ill, and 7) Among the most extremely ill patient. The CGI-I is used to measure improvement in illness and also uses a 7 point Likert scale: 1) Very much improved, 2) Much improved, 3) Minimally improved, 4) No change 5) Minimally worse, 6) Much worse, 7) Very much worse. The PI or a designated study staff will administer this at time points as per the schedule of events.

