Screening Visit: Screening visit assessments includes: Fasting blood samples for lipid profile, comprehensive metabolic profile, CBC, hs-CRP, IL-6 and TNF-α will be obtained at the screening visit. Potential subjects will undergo a diagnostic evaluation. Psychiatric diagnosis will be determined using the Mini International Neuropsychiatric Interview (MINI). A medical evaluation, including weight, height, vital signs, a physical examination, and review of systems will be performed. A urine pregnancy test will be performed on all women of childbearing potential. The subjects will be given an appointment card for their next visit which will also provide a reminder for the use of appropriate birth control. In addition, a urine drug screen, and a 12-lead EKG will be performed. A 30-day timeline follow-back will be administered at screening visit to assess current substance use and Fagerstrom test will assess smoking status.

Following the screening visit and prior to baseline visit, the subject's primary care provider and/or psychiatrist will be notified of their participation in the study in order to adequately screen subjects, ensure that only eligible subjects are enrolled, and minimize subject risk.

All screening procedures will be completed and reviewed by PI for eligibility criteria prior to randomization/baseline visit.

Randomization: After completion of all screening assessments, all patient eligibility screening documents will be sent to UMass for review and eligibility confirmation. Once a patient is deemed eligible, a randomization ID and a randomization condition (brexpiprazole versus control) for the subject will be generated. The randomization condition will be accessible to the site and their pharmacy and will be used to prepare the corresponding study treatment. Once a subject has been assigned a randomization ID, they will be identified in the CRF by this randomization ID for the duration of their study participation.

Baseline Visit: Subjects will be randomly assigned to switch to brexpiprazole (brexpiprazole group) or remain on the same antipsychotic medication (control group).

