Study intervention: Brexpiprazole switch: For the brexpiprazole group, an overlap and taper switch method will be used. The current antipsychotic medication will be tapered following standard clinical practice and discontinued over a time period of 6 weeks. Brexpiprazole will be started at 1mg/day for 4 days, and 2mg/day for 3 days, and then titrate by up to 1mg/day increase every 3 days to reach 4mg/day, or as much and as fast as the participant can tolerate. Participants will stay on 4mg/day or the highest tolerable dose until the end of the study.

Medication adherence will be measured via pill counts at weekly visits. The study staff will discuss pill count data with participants to emphasize the need to take the study medication.

If participants cannot tolerate brexpiprazole after randomization, it will be stopped, though the participant may continue to be followed on another treatment (ideally their pre-study antipsychotic medication) for the remaining weeks of the study. The subject will then continue the rest of the study on their previous antipsychotic medication.

The following assessments will be completed at baseline visit:

- 1) Anthropometric measures (weight, waist circumference and height at screening to be used) and Vital signs
- 2) Weekly TLFB
- 3) Drug screen
- 4) Post-Screening Pregnancy Checklist
- 5) AE review
- 6) PANSS, SANS, QLS, CGI-S
- 7) C-SSRS, EPS scales, CDRS
- 8) Supportive counseling

Week 6 and week 12 visits: The following assessments will be done at week 6 and 12.

- 1) Anthropometric measures (weight, waist circumference) and Vital signs
- 2) Weekly TLFB
- 3) Drug screen
- 4) Post-Screening Pregnancy Checklist (Week 6 only)
- 5) AE review
- 6) PANSS, SANS, QLS, CGI-S
- 7) C-SSRS, EPS scales, CDRS
- 8) Supportive counseling
- 9) ECG
- 10)Labs (CMP, CBC, lipid panel)
- 11)Labs hs-CRP, IL-6 and TNF-alpha collected and stored at -80F
- 12)Fagerstrom test

Week 2, 3,4,5,7,8,9,10,11 visits: These visits may be completed virtually through a secured platform depending on the most current COVID situation. During the virtual routine follow up visits, vital signs and urine drug screen will be unable to be collected; but all subjects who go through the switch will have demonstrated no clinically significant changes in vitals, ECG, or lab results in prior long visits. The following assessments will be administered at these weekly visits:

- 1) Vital signs and anthropometric measures (weight)
- 2) Urine drug screen

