If the subject is terminated from the study on what would be their week 6 visit, they will complete all the assessments that are required in a regular week 6 visit. If the subject is terminated from the study at any other point, only safety procedures will be performed (listed below).

- 1. Vital signs and anthropometric measures (weight)
- 2. Urine drug screen
- 3. TLFB
- 4. AE review
- 5. Safety labs (CMP, CBC, lipid panel)
- 6. ECG
- 7. CSSRS

G. TREATMENT OF SUBJECTS

Study Drug Dose and Administration

The study drug brexpiprazole (Rexulti) will be administered orally. Subjects will be randomly assigned to either switch to brexpiprazole or remain on the same antipsychotic medication (treatment as usual). Subjects randomized to brexiprazole treatment will be titrated as per section F (study intervention). Study participants randomized to brexpiprazole treatment will be titrated to 4mg/day or the highest tolerable dose as per the study MD's clinical judgement until the end of the study. Dose de-escalation due to tolerability will be allowed in the study. If subjects recover, the dose can be increased to the 4mg or the highest tolerable dose as per the MD's clinical judgement. Patients who are unable to tolerate a minimum dose of 1 mg will be withdrawn from the study

Study Drug

Commercially available brexpiprazole will be provided directly to all sites by Otsuka Pharmaceuticals. Study drug will be provided as 1mg and 2mg tablets. Subjects will take medications as dispensed by their site's Investigational drug pharmacy.

Storage and Drug Accountability

The study drug will be stored as per the drug insert. The sites are required to maintain current drug dispensation and accountability logs throughout the study. All unused supplies will be checked against the drug movement records during the study and/or at the end of the study.

Prohibited Medications

Currently on the following antipsychotics

- Aripiprazole
- Cariprazine

Currently on medications to treat substance use such as:

- Disulfiram,
- Naltrexone,
- Acamprosate,
- Methadone,
- Buprenorphine,
- Varenicline
- Bupropion

Special Consideration for Concomitant Medications with Brexpiprazole

Medications	Intervention
-------------	--------------

Strong CYP3A4 inhibitors	With concomitant use of brexpiprazole with a
	strong CYP3A4 inhibitor, reduce the brexpiprazole
Examples: itraconazole,	dosage and administration [see drug insert
clarithromycin, ketoconazole	dosage and administration (2.5)]

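### The closed early-termination list in Section F leaves out the craving VAS that Table 1 requires at that visit; adding symptom and quality-of-life ratings there would be a cheap improvement

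*Combined protocol and SAP*

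**What the plan says.** The second primary objective is the effect on substance craving, measured by the VAS (Synopsis; Section C). Table 1 in Section E marks the VAS in all 15 columns: screening, weeks 0 to 12, and early termination. The VAS paragraph in Section E points the same way: "The VAS will be used to assess craving for substance use as per the schedule of events".

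Section F, Early Termination Visit, sends an exit at week 6 to the regular week 6 assessments. For every other exit it says: "If the subject is terminated from the study at any other point, only safety procedures will be performed (listed below". Seven items follow: vital signs with weight, urine drug screen, TLFB, adverse events, safety labs, ECG and C-SSRS. The VAS is not among them. Footnote 5 to Table 1 makes the same split between week 6 and other visits: "If ET falls on any other visit, follow ET protocol".

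Table 1 marks the PANSS, SANS, CDRS, CGI and QOL at weeks 0, 6 and 12 only, with the CGI-I omitted at baseline, and leaves the early-termination column blank for all of them. Section E repeats this for individual scales, for example: "Designated study staff will administer the SANS at baseline, week 6 and week 12". Section F agrees.

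Section D expects 20% discontinuation: 50 randomized and 40 completing. Section L analyses craving, symptoms and quality of life by intention to treat in a mixed model over the full 12 weeks, with baseline measures of substance use and clinical symptoms as covariates.

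**The concern.** There are two matters, of different kinds.

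The first is a contradiction. One section requires a primary outcome at the exit visit. Another limits that visit to a list without it. Whether the last craving value of a leaver is obtained then depends on which section the site has open, and the study has four sites.

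The second is a gap on which Table 1 and Section F agree, so it is a design choice. A subject who leaves in weeks 1 to 5 has a baseline rating on each symptom and quality-of-life scale and no scheduled rating afterwards. With baseline used as a covariate, such a subject has no outcome value to contribute to the group comparison on that scale, although the analysis is labelled intention to treat.

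**Working it through.** **Step 1. The early-termination visit, line by line.** Nine rows of Table 1 are marked in the early-termination column.

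| Table 1, early termination | Section F list |
|---|---|
| Vital signs | yes |
| Weight | yes |
| Urine drug screen | yes |
| TLFB | yes |
| Adverse events | yes |
| Labs (CMP, lipid panel, CBC) | yes |
| ECG | yes |
| C-SSRS | yes |
| Craving VAS | **no** |

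Eight of the nine agree, and the VAS is the only difference. The list also contains the TLFB, which Section E places under efficacy, so its description as safety procedures does not fit its own content.

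**Step 2. The other Section F lists.** None names the VAS: not the screening text ("A 30-day timeline follow-back will be administered at screening visit to assess current substance use and Fagerstrom test will assess smoking status" is as near as it comes), nor the baseline list, the week 6 and 12 list ("The following assessments will be done at week 6 and 12"), or the weekly list ("Week 2, 3,4,5,7,8,9,10,11 visits: These visits may be completed virtually"). Week 1 appears in no list. These lists are incomplete in other ways too. Drug dispensing, marked at seven visits in Table 1, is missing from all of them. The screening text lacks the C-SSRS and HbA1c. The week 6 and 12 list lacks the CGI-I, which footnote 2 excludes at baseline only ("CGI-I will not be administered at baseline. Only CGI-S is administered at baseline"). They read as abbreviations, and unlike the early-termination text they do not say that only the listed items are done.

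**Step 3. The plan's own figure.** 40 / (1 − 0.20) = 50, as stated in Section D. Expected exits: 50 × 0.20 = 10. The documents do not give their timing.

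**Step 4. VAS readings at stake.** There is one early-termination reading per leaver, so at most 10. Forty completers give 40 × 12 = 480 post-baseline readings.
- All exits at week 1: 10 / (480 + 10) = 10/490 = 2.0%.
- All exits at week 11, each with ten earlier weekly readings: 10 / (480 + 100 + 10) = 10/590 = 1.7%.

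This assumes that the exit visit takes the place of that week's visit and that all leavers attend it. In the week 1 case the exit reading is each leaver's only post-baseline VAS.

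**Step 5. Subjects without a scheduled post-baseline rating.** This depends only on how many leave in weeks 1 to 5: from 0 of 50 (all leave at week 6 or later) to 10 of 50, or 20% (all leave earlier). If exits were spread evenly over weeks 1 to 11, an assumption, the figure would be 10 × 5/11 = 4.5.

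**Step 6. What ratings at early termination would add.** Per scale, 0 to 10 values.
- All exits in weeks 1 to 5: completers give 40 × 2 = 80 scheduled ratings, so the added share is 10 / (80 + 10) = 11.1%.
- All exits in weeks 7 to 11: leavers also have week 6, so the share is 10 / (80 + 10 + 10) = 10.0%.
- All exits at week 6, or no leaver attends: 0.

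**The case against.** The strongest reply is that the VAS question is already answered. Section E ties the VAS to the schedule of events, and Table 1 is explicit. Section F never names the VAS at any visit, so treating its lists as controlling would mean that a primary outcome is never collected, which cannot be intended. This stands for the screening, baseline, weekly and week 6/12 lists. A reader might infer from Section F that craving data are lost throughout the trial; the documents do not support that. The reply does not dispose of the early-termination text, which is exclusive in its wording and otherwise matches the Table 1 column. Nor does any passage say in general which section governs.

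On the symptom and quality-of-life ratings, the reply is that the plan is consistent and that ratings taken at exit bring a problem of their own: off schedule, they come only from leavers, so their timing may be informative and could distort the fitted time trend. Both points stand. They are why this part is offered as an improvement and paired with a sensitivity analysis.

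Three stronger readings should be set aside:
- A reader might infer bias in the group comparison. The documents give neither the number, the timing, the arm nor the reasons of exits, so no direction or size can be stated.
- A reader might charge the missing exit ratings with the precision lost in going from 50 subjects to 40. That loss is the dropout which Section D already anticipates. What exit ratings would recover is smaller and cannot be computed from the documents.
- A reader might see a contradiction between the PANSS-based withdrawal rule, which applies throughout the study, and a PANSS schedule of three visits. The documents do not bar an unscheduled PANSS, so the rule and the schedule can coexist.

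**Conclusion.** The contradiction at early termination is real and needs correcting: it concerns a primary outcome and the remedy is a change of wording. Its size is at most 10 VAS readings, 1.7% to 2.0% of those after baseline, on the planned 20% discontinuation. It matters most for a subject leaving at week 1. No loss of data is shown, since a site working from Table 1 would collect the reading. The TLFB, the other primary measure, is collected at early termination under both sections and is not affected.

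The missing exit ratings on the five secondary scales are a gap and not an error. They leave 0 to 10 of 50 subjects without a scheduled post-baseline value. That these subjects would not inform the comparison rests on baseline entering as a covariate, as Section L says for clinical symptoms; Section L does not say so for QOL, and the same treatment is assumed here.

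One neighbouring matter should be raised as its own point. Section F (Study intervention) allows a subject who cannot tolerate brexpiprazole to remain in follow-up, while Section G (Study Drug Dose and Administration) withdraws those unable to tolerate the minimum dose. The two passages must be reconciled.

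**What to change.** 1. In Section F, Early Termination Visit, add the VAS to the list and replace the wording that restricts the visit to safety procedures.
2. Add one sentence stating that Table 1 governs which assessments are done at each visit. This settles the remaining Section F lists, including the absent week 1 list, without rewriting each one.
3. As an improvement, add the PANSS, SANS, CDRS, CGI-S/CGI-I and QOL to the early-termination visit in both Table 1 and Section F, for subjects who attend and agree.
4. In Section L, enter these exit ratings in the mixed model at their actual time, pre-specify a sensitivity analysis using only the scheduled week 6 and 12 ratings, and report both.

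The cost is one amendment with IRB re-approval (Section K). Items 1 and 2 are text changes and add no visits. Item 3 lengthens an exit visit that already includes labs, ECG, C-SSRS and TLFB, using scales already in the study, for at most about 10 subjects. Fewer would be reached in practice. The document is dated January 2022, in an enrollment window planned from February 2018 to November 2023, so about two-thirds had passed (1,422 of 2,104 days = 68%). If exits were even over that window, an assumption, about 3 of the 10 would remain. Nor can the change reach subjects who withdraw consent (Section H) or do not attend.

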- 2) Meets the DSM-5 criteria for diagnoses of schizophrenia or schizoaffective disorder and substance use disorder (alcohol, cocaine, heroin, or cannabis) based on the Mini International Neuropsychiatric Interview (MINI).
- 3) Uses substance on at least 4 of the previous 30 days prior to randomization with at least one use in the week prior to randomization for one of the substances (cocaine, heroin, marijuana or alcohol) as assessed by the TLFB interview
- 4) Stable dose of antipsychotic agent for at least one month
- 5) Well established compliance with outpatient medications
- 6) Female subjects of child-bearing potential are required to practice appropriate birth control methods during the study.
- 7) Male subjects who are sexually active must agree to use appropriate birth control measure to avoid partner pregnancy

Exclusion criteria:

Each subject must not have the following exclusion criteria prior to randomization in the study.

- 1) Psychiatrically unstable
- 2) Currently meets DSM-5 criteria for any substance use disorder other than caffeine, nicotine, alcohol, cocaine, heroin and cannabis.
- 3) Significant, unstable medical conditions including severe cardiovascular, hepatic, renal or other medical diseases
- 4) History of a seizure disorder
- 5) Pregnancy or breastfeeding
- 6) Currently on aripiprazole or cariprazine
- 7) Currently on medications to treat substance use (disulfiram, naltrexone, acamprosate, methadone, buprenorphine, varenicline or bupropion)
- 8) Patients previously exposed to brexpiprazole

Exclusionary Lab values:

Comprehensive Metabolic Panel					
Sodium	<1.1 times the lower limit or >1.1 times upper				
limit of the reference range					

Potassium	<1.1 times the lower limit or >1.1 times upper limit of the reference range
Blood Urea Nitrogen (BUN)	>1.3 times upper limit of the reference range
Creatinine	>1.3 times upper limit of the reference range
Aspartate amino transferase (AST)	>3 times upper limit of the reference range
Alanine amino transferase (ALT)	>3 times upper limit of the reference range
Glycated Hemoglobin (HbA1c)	Patients with a value > 9.0% (at screening only)
eGFR	< 35 ml/min

E. SCHEDULE OF EVENTS AND STUDY ASSESSMENTS

Table 1. Schedule of Events

Procedu re	Visit	Screening	Visit 1 (basel ine)	Visit 2	Visit 3	Visit 4	Visit 5	Visit 6	Visit 7	Visit 8	Visit 9	Visit 10	Visit 11	Visit 12	Visit 13/EO T	Early Termin- ation (ET)

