- 3) Post-Screening Pregnancy Checklist (Week 3 and 9 only)
- 4) TLFB
- 5) AE review
- 6) Supportive counseling

End of Study / Discontinuation of Study Medication – When a participant who is randomized to brexpiprazole completes Visit 12 (or sooner for those discontinuing study medication), he or she will no longer receive medications through the study. There will need to be a discussion with the participant and his/her treatment provider as to whether or not the participant will continue on the study medication after the subject's study participation is over. For participants finishing the study at Visit 12, this discussion should occur about three weeks prior to the final visit. If the participant will continue on the study medication study medications following standard clinical practice. The monitoring and management of symptoms, therapeutic response and medication side effects will be the responsibility of the treatment provider.

Subjects who do not wish to continue on the study medication after the end of study, the treatment provider can begin to manage a cross titration off the study medication and on to either the antipsychotic medication prior to the study or a new antipsychotic medication following standard clinical practice. The monitoring and management of symptoms, therapeutic response and medication side effects will be the responsibility of the treatment provider.

Withdrawal of Subjects

Subjects are free to discontinue their participation in the study at any time and without prejudice to further treatment. The investigator must withdraw any subject from the study who requests to be withdrawn or fits the criteria below:

- 1) If subject meet any exclusion criteria after enrollment.
- 2) If subjects have laboratory results that meet the exclusionary criteria range during the study, the subject will have his/her labs repeated before being withdrawn from the study.
- 3) Subjects will be withdrawn from the study is there is an increase in their PANSS total score greater than or equal to 20 compared to their baseline total score at any point during the study.
- 4) Female subjects may be terminated from the study if they become pregnant at any time while participating in the study.
- 5) If at any time the study sponsor or research personnel at UMass decide to terminate the study, subjects' consent will be withdrawn involuntarily.

Early Termination Visit

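### The protocol both keeps in the study and withdraws a subject who cannot tolerate 1 mg brexpiprazole, and its outcome-related withdrawal rules end data collection that the 12-week intent-to-treat analysis would use

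*Combined protocol and SAP*

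**What the plan says.** Two places tell sites what to do when brexpiprazole is not tolerated.

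- Section F, Study intervention: the drug is stopped, and "the participant may continue to be followed on another treatment". The next sentence is firmer: "The subject will then continue the rest of the study on their previous antipsychotic medication".
- Section G, Study Drug Dose and Administration, after allowing dose reduction: "Patients who are unable to tolerate a minimum dose of 1 mg will be withdrawn from the study".

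On dose, section F says "Brexpiprazole will be started at 1mg/day for 4 days" and section G says "Study drug will be provided as 1mg and 2mg tablets".

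Section F, Withdrawal of Subjects, covers both arms: "The investigator must withdraw any subject from the study who requests to be withdrawn or fits the criteria below". Rule 1 reads "If subject meet any exclusion criteria after enrollment". Rule 3 is a rise of 20 or more in PANSS total over baseline. The exclusion criteria in section D include "Psychiatrically unstable" (item 1) and current use of a medication for substance use (item 7).

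An early termination visit at week 6 follows the full week 6 schedule. At any other time it is a short safety list that includes one TLFB but no psychiatric or quality-of-life scales. Table 1 also marks VAS at that visit; the section F list does not. No visit is scheduled after it. Section H ends data collection for subjects who withdraw consent.

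Section L plans an intent-to-treat mixed model, described as estimating pragmatic effects, over all 12 weeks including the switch phase. Baseline substance use and symptoms are the named covariates. No missing-data assumption or sensitivity analysis is given.

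**The concern.** An intent-to-treat comparison needs outcomes from randomised subjects whether or not they stay on treatment. Stopping the drug and stopping data collection are separate decisions, and the Study intervention paragraph treats them so. Section G and the withdrawal rules merge them. Subjects who have not withdrawn consent then lose outcomes that cannot be recovered later, for reasons tied to tolerability or to the outcomes themselves.

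The 1 mg rule can act only in the brexpiprazole arm, so whatever it removes is removed from one side. The withdrawal rules act in both arms but select subjects who are doing badly, or whose clinician has started a substance-use medication.

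Any dropout already makes the mixed model rely on data being missing at random; these rules add to that reliance. For PANSS itself, withdrawal on an observed PANSS value is compatible with the assumption. For TLFB and VAS it is less secure, because those models carry baseline symptoms but not the later PANSS value that triggers removal.

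**Working it through.** **Do the two intolerance rules meet in the same subject?** Dose reduction is allowed, treatment starts at 1 mg, and no smaller tablet is supplied. A subject who cannot take brexpiprazole at all is therefore, in practice, one who cannot take 1 mg. Section F keeps that subject in the study; section G removes the subject. Treating section G as the specific exception does not help, since it would leave section F's rule with almost nobody to apply to.

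**The plan's own figure.** Section D: 40 completers with 20% discontinuation gives 40 / (1 - 0.20) = 50 randomised, which matches. The expected 50 - 40 = 10 non-completers are from all causes, including consent withdrawals that no rule change can recover.

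**Records lost per subject.** There are 12 post-baseline weekly TLFB/VAS records and two post-baseline scale visits (weeks 6 and 12). An exit in week w, with that week's record kept, loses 12 - w weekly records.

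| Exit | Weekly records lost | Scale visits lost |
|---|---|---|
| 1 mg rule, week 1 | 12 - 1 = 11 | 2 of 2 |
| PANSS rule, week 6 | 12 - 6 = 6 | 1 of 2 |
| PANSS rule, week 12 | 0 | 0 |
| Exclusion criterion met in week w | 12 - w | depends on w |

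Eleven is the upper case for the 1 mg rule. A subject who fails at 1 mg after a later dose reduction loses fewer. PANSS is scheduled only at baseline, week 6 and week 12, so rule 3 acts in practice at week 6, when the full battery is collected.

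Against 50 x 12 = 600 planned records, two week 1 exits cost 22 (3.7%) and two week 6 exits cost 12 (2.0%). The count of two is an assumption.

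**Illustration for the 1 mg rule; all inputs assumed.** 25 per arm; an effect reaching -1.2 days per week by week 6; k brexpiprazole subjects leave in week 1 and would have returned to the control mean. The target is the mean difference over weeks 7 to 12.

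- With full follow-up the difference is -1.2 x (25 - k)/25.
- With withdrawal the model estimates -1.2 from those who remain.
- Overstatement = 1.2k/25.

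| k | Full follow-up | Withdrawn | Overstatement |
|---|---|---|---|
| 1 | -1.152 | -1.200 | 0.048 (4.2%) |
| 2 | -1.104 | -1.200 | 0.096 (8.7%) |
| 3 | -1.056 | -1.200 | 0.144 (13.6%) |

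A quadratic group-by-time model gives 0.049, 0.098 and 0.147. With no true effect, every row is zero.

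**Standard error.** Assumed random intercept SD 1.6, random slope SD 0.05 or 0.10, residual SD 1.5. Without a baseline covariate the standard error is 0.50 to 0.57 days. With the baseline substance-use adjustment that section L specifies, it is about 0.38 to 0.46. The largest ratio is 0.147/0.384 = 0.38 standard errors.

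**Illustration for the PANSS rule; all inputs assumed.** If PANSS change is normal with SD 10 to 15, the chance of a rise of 20 or more is 2.3% to 9.1% at mean change 0 and 6.7% to 15.9% at mean change +5. If the arms differ by those 5 points, and withdrawn subjects then use one more day per week, the bias is the difference in proportions times 1 day: 0.067 - 0.023 = 0.044 at SD 10, and about 0.067 at SD 15. It favours whichever arm has the worse PANSS course, and is zero if PANSS change is equal.

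**The case against.** The withdrawal rules differ in kind from the section F and G conflict. They look like deliberate safety rules in a 50-subject proof-of-concept study and contradict no other instruction. That stands: changing them is a design improvement, while the conflict is a drafting error.

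Rule 1 cannot be literal. Exclusion 8 is previous exposure to brexpiprazole, which would remove every treated subject. Some criteria must apply at entry only, and the protocol does not say which, so losses under rule 1 are less certain than those under rule 3. Rule 2 (repeat laboratory tests) is a laboratory safety rule with no shown link to the outcomes, and pregnancy has its own text in sections F and H. Neither belongs in this point.

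A reader might infer more than the documents support:

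- That the result will be materially biased, or biased towards brexpiprazole. No frequency, SD or effect size is given; the illustrations are modest and can be zero or go either way.
- That section L promises follow-up after withdrawal. Its 12-week sentence settles that switch-phase data are analysed, and a mixed model can keep a withdrawn subject's earlier data in the randomised arm. The point is that available data are cut short.
- That sites were given different instructions. All share one inconsistent protocol, and lead-site training, monitoring and a medical monitor (section J) should narrow differences in handling. They do not remove the conflict.
- That section F guarantees complete data. Its first sentence is only permissive.

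**Conclusion.** The point holds and should be fixed. Sections F and G conflict for a subject who cannot tolerate 1 mg, and the section G rule acts in one arm only. Withdrawal rules 1 and 3 end follow-up in either arm for outcome-related reasons. The loss per subject is up to 11 of 12 weekly records under the 1 mg rule and 6 of 12 under the PANSS rule at week 6; these counts follow from the visit schedule.

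The effect on the estimate cannot be derived from the documents. Under the assumed inputs, the 1 mg rule overstates the effect by 0.05 to 0.15 days, at most about 0.4 standard errors with the planned baseline adjustment. The case rests on an operational contradiction and avoidable, unrecoverable loss of data in a small trial; a large bias has not been shown.

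**What to change.** 1. Section G: a subject who cannot tolerate 1 mg stops brexpiprazole and stays in the study on the previous antipsychotic. In section F, make the permissive follow-up sentence mandatory, subject to consent.
2. Section F, withdrawal rules 1 and 3: meeting the criterion ends brexpiprazole, or frees the clinician to change treatment in either arm, but does not end data collection. Subjects who have not withdrawn consent continue the scheduled weekly TLFB and VAS and the week 6 and week 12 scales where clinically feasible, and these data enter the intent-to-treat model.
3. Limit rule 1 to criteria that can arise after entry, which excludes item 8. Leave rule 2 and the pregnancy rules as they are, or align the pregnancy text in sections F and H explicitly.

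Costs: section K requires IRB re-approval. The synopsis expected first enrolment in February 2018 and this version dates from January 2022, so subjects already enrolled will have been followed under the existing rules. Some continued visits will be with unwell subjects. Section F allows virtual weekly visits only in connection with COVID, and that wording would need widening. Data after a treatment change will include the new treatment's effect, which suits a pragmatic intent-to-treat comparison. No added patients or procedures are needed, and consent withdrawals remain lost.
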